## 4.4. Summary of Known Benefits and Potential Risks

#### 4.4.1. Potential Benefits

Participants will receive active investigational product or phosphate-buffered saline injection (placebo). The effects of XT-150 for FJOA have not been previously explored, however potential therapeutic benefits of XT-150 for the treatment of FJOA pain are:

- Increased mobility for many weeks following a single dose of XT-150
- Reduction in requirement for pain medications and therapies
- Reduction in pain symptoms for many weeks following a single dose of XT-150.

## 4.4.2. Known Risks

Intra-articular injection in the knee with XT-150 has been well tolerated in clinical trials of OA pain. Based on multiple animal studies and 4 clinical trials in osteoarthritis, XT-150-related adverse events are most commonly minor injection site reactions.

#### 4.4.3. Potential Risks

Nonclinical studies and clinical studies with XT-150 are described in the IB. XT-150 posed minimal risk in these studies. General risks associated with IA injection are injection site reactions and infection, which will be explicitly captured in follow-up safety assessments.

## 4.4.3.1. Safety of DNA as a Therapeutic Agent

DNA as a therapeutic agent has been well tolerated. The main theoretical safety concerns regarding the clinical use of DNA are that they might integrate with the host/patient DNA, or that injection of foreign DNA might stimulate anti-DNA antibodies or an autoimmune reaction (Prazeres 2014).

With both DNA vaccines and DNA plasmids, the risk of integration was repeatedly found to be low with years of research into the possibility (FDA 2007; Prazeres 2014). With plasmids, the potential for integration has been removed by excluding any sequences that might drive homologous recombination and integration into the genome. In fact, excluding these elements lowers the risk of plasmid integration to less than the rate of naturally occurring mutations (Prazeres 2014). XT-150 has been designed to transiently express a variant of human IL-10 without integrating into the genome.

Immunogenicity of DNA appears to be low (Ferraro 2011), and correlates to the lack of success of DNA agents (even pathogenic bacterial sequences) as vaccines. No link has been found between plasmid DNA injections and any clinical markers of autoimmunity (Prazeres 2014). In addition, DNA plasmids have been used in research and development for 25 years. Synthetic vectors share the non-infectious properties of viral vectors and elicit low immunogenicity and lower toxicity compared to viral vectors (Xu 2011; Gôrecki 2006).

## 4.4.4. Safety of Interleukin-10

Published studies in the literature have reported IL-10 protein therapy to be safe in humans. The safety of IL-10 protein injections was studied in healthy volunteers at doses up to  $100 \,\mu\text{g/kg}$ . Details of these studies can be found in the IB.

After injection in healthy volunteers at doses up to 100 µg/kg, wild-type human IL-10 protein was found to be rapidly degraded with a half-life of 2.0 to 4.5 hours (Chernoff 1995; Huhn 1996; Huhn 1997; Milligan, 2005). In the Huhn, 1997 study, after intravenous administration of high doses of IL-10 protein (100 µg/kg), 42% (15/36) of the volunteers experienced flu-like adverse effects, the most common of which were headache (11/36 participants, 31%), fever (5/36, 14%), and back pain (3/36, 8%). Pharmacodynamic effects from intravenous IL-10 treatment included transient increases in neutrophils and monocytes, and decreases in lymphocytes, which peaked around 6 hours after injection (Chernoff, 1995). When given intravenously, IL-10 was also found to inhibit production of the cytokines IL-1 $\beta$  and tumor necrosis factor-alpha (TNF- $\alpha$ ), and reduce T-lymphocyte stimulation.

Recombinant human IL-10 has been clinically tested as a therapy in humans in a number of indications without serious or irreversible side effects. In these trials, IL-10 injections of up to 25  $\mu$ g/kg were reported to be well tolerated. With chronic intravenous and high doses, statistically significant hematological changes were observed, as well as fever. Adverse events of neutrophilia, headache, injection site pain, anemia, and nausea were observed with daily dosages in patients with Crohn's Disease.

As an anti-inflammatory agent, the biological activity of IL-10 is different than that of other interleukins. Exogenous IL-10 is the only interleukin shown to be well tolerated. However, the anti-inflammatory activity of IL-10 treatment could mask latent infections (Moore, 2001). Since IL-10 has been theorized to mask latent infections, any participant who has a current autoimmune condition or documented immunodeficiency, has a history of immunosuppression, or is currently receiving treatment with immunosuppressive agents is excluded from this study.

Note that XT-150 is a sterile aqueous formulation of a plasmid designed to transiently express a proprietary variant of IL-10. XT-150 expression of the variant IL-10 is expected to be safer than systemic injection of active IL-10 protein as therapy for the following reasons:

- Rather than injections of IL-10 protein, XT-150 treatment will result in IL-10v levels that exist transiently and at a much lower concentration.
- The IL-10v levels from XT-150 expression will be localized in the intra-articular joint space. Low systemic levels of IL-10 from XT-150 treatment may be present for short periods of time and if present are unlikely to lead to adverse effects,

## 4.4.5. Possible Anticipated Adverse Events and Clinical Monitoring

Anticipated AEs for which there will be specific safety monitoring in humans will be based on the preclinical studies as well as the published reports of studies of IL-10 protein injections to healthy volunteers. In a publication of the incidence and characteristics of intra-articular facet joint injection by Kim, 2020, the incidence of major procedure-related complications, such as local injections site infection, was demonstrated to be

very low (< 1%). Aseptic technique will be used, and the investigators are highly trained and experienced in the administration of intra-articular injections.

Based on published reports of IL-10 protein injections in humans, the following AEs could be attributed to XT-150-produced IL-10v. IL-10 protein doses were more than 1000-fold higher than can be expected with XT-150.

- Minor decreases in neutrophils and T-lymphocytes.
- Changes in hemoglobin, platelet counts, and leukopenia
- Flu-like adverse effects related to IL-10, including symptoms of headache, and fever, chills, nausea, and myalgias, as reported by Chernoff, 1995, Huhn, 1996, Huhn, 1997, and van Deventer, 1997.

None of these AEs have been recorded for participants across all clinical studies following knee injections with XT-150 doses up to  $600 \mu g$ , including 0201 study participants who received a second injection in the 0203 study.

[figure not shown]

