# 10.7. Adverse Events of Special Interest

#### 10.7.1. Adverse Events of Noted Interest in IL-10 Protein Trials

Safety will include the following reported IL-10 protein-associated toxicities as defined by CTCAE (v5.0). Systemic levels of XT 150 produced IL-10 protein are expected to be more than 1000-fold lower than when given as a protein solution (Huhn, 1997); and XT-150 will be predominately localized to the facet joint space.

• Grade 1 (unexplained) fever – 38.6°C to 39°C

- Grade 2 allergic, cytokine release, or infusion-related reactions Therapy or infusion interruption indicated but responds promptly to symptomatic treatment (e.g., antihistamines, NSAIDS, narcotics, IV fluids); prophylactic medications indicated for <24 hours
- Grade 2 injection site reaction Pain; lipodystrophy; edema; phlebitis
- Grade 2 neutropenia <1500 to 1000/mm3; <1.5 to 1.0 x109/L

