#### 10.14.1. Adverse Events

AEs will be coded to system organ class (SOC) and preferred term according to MedDRA, version 24.1. Pretreatment AEs are defined as AEs that have an onset on or after the date the informed consent was signed but before the date of the first dose of study drug. Treatment-emergent adverse events (TEAEs) are defined as AEs that start or worsen after the first dose of study drug. Adverse event severity will be graded using CTCAE v5.0.

Summaries will be provided for TEAEs, with the number and percentage of participants reporting each type of event presented. If a participant reports the same preferred term more than once, it is counted only once within that category. Similarly, if a participant has AEs of two or more preferred terms under the same SOC, then that participant only counts once for that SOC. Furthermore, for a given summary, the preferred term will only be counted once at its worst severity and strongest relationship to study drug.

AEs of special interest will be identified programmatically and reviewed by the study team prior to unblinding. AEs of special interest include:

- (Unexplained) fever
- Grade 2+ allergic, cytokine release, or infusion-related reactions Therapy or infusion interruption indicated but responds promptly to either:
  - symptomatic treatment (e.g., antihistamines, NSAIDS, narcotics, IV fluids)
  - prophylactic medications indicated for  $\leq$ 24 hours
- Grade 2+ injection site reactions
- Grade 2+ neutropenia

The following summaries and listings for AEs will be provided:

- An overall summary table of AEs summarizing the number and percent of participants, in the following categories: any AE, any TEAE, TEAEs by highest severity grade, any TEAEs of special interest, TEAEs by relationship to study drug (related, not related), any serious TEAE, TEAEs leading to drug withdrawal, and TEAEs leading to premature withdrawal from the study, any TEAEs with a fatal outcome
- Incidence of TEAEs by MedDRA SOC and preferred terms
- Incidence of TEAEs by MedDRA SOC, preferred terms, and maximum severity grade
- Incidence of TEAEs by MedDRA SOC, preferred terms, and relationship to study drug.

- Incidence of TEAES of special interest, by SOC, preferred terms, and maximum severity grade.
- Incidence of SAEs by SOC, preferred terms, and maximum severity grade
- Listing of all AEs (with non-treatment-emergent events flagged and AEs of special interest highlighted).
- Listing of all AEs of special interest

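### Of the five flu-like symptoms that Protocol 4.4.5 links to IL-10v, the special-interest lists name only fever, and no planned row counts participants with any flu-like reaction

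*Protocol*

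**What the plan says.** Protocol 4.4.5 opens by saying "Anticipated AEs for which there will be specific safety monitoring in humans will be based on the preclinical studies" and on published reports of IL-10 protein given to healthy volunteers. A later paragraph says "the following AEs could be attributed to XT-150-produced IL-10v". It lists blood-count changes and then the flu-like group: "Flu-like adverse effects related to IL-10, including symptoms of headache, and fever, chills, nausea, and myalgias". The same section expects IL-10 doses in those reports to exceed XT-150 exposure more than 1000-fold. It also reports that none of the listed events was recorded after knee injections of XT-150 up to 600 µg.

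Protocol 4.4.4 gives figures for one protein study at 100 µg/kg: "42% (15/36) of the volunteers experienced flu-like adverse effects", with headache in 11, fever in 5 and back pain in 3 of the 36.

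Protocol 10.7.1 is headed as events of interest from IL-10 protein trials. It lists four items: Grade 1 unexplained fever; Grade 2 allergic, cytokine-release or infusion-related reactions; Grade 2 injection-site reaction; and Grade 2 neutropenia. SAP 10.14.1 repeats the four, with no grade on fever and Grade 2+ on the other three. It adds that "AEs of special interest will be identified programmatically and reviewed by the study team prior to unblinding".

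SAP 10.14.1 also plans TEAE tables by system organ class (SOC) and preferred term, by maximum severity and by relationship, and a listing of all AEs. A participant counts once per preferred term and once per SOC.

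**The concern.** Safety and tolerability is the primary objective. A reader who wants to know whether locally injected XT-150 produces systemic IL-10 effects will look first at the special-interest table. That table has a line for fever but none for headache, which was the most frequent flu-like effect in the protocol's own reference data, and none for chills, nausea or myalgia. In the ordinary TEAE tables these symptoms fall under separate preferred terms. A participant with headache, nausea and myalgia appears in several rows, and adding the rows counts that participant several times. With 24 participants per arm, a modest excess spread over several terms could be overlooked, although every event is in the database.

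**Working it through.** **Inputs.** Symptom list: Protocol 4.4.5. Volunteer counts: Protocol 4.4.4. Special-interest items: Protocol 10.7.1 and SAP 10.14.1. Counting rule: SAP 10.14.1. Arm size 24, so 48 on active drug: SAP 5.2.

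**1. The protocol's figures reproduce.** 15/36 = 41.7% (stated 42%); 11/36 = 30.6% (31%); 5/36 = 13.9% (14%); 3/36 = 8.3% (8%).

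**2. Symptom list against special-interest lists.**

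| Symptom in 4.4.5 | Named in Protocol 10.7.1 | Named in SAP 10.14.1 |
|---|---|---|
| Headache | no | no |
| Fever | yes (Grade 1, unexplained) | yes (unexplained, no grade) |
| Chills | no | no |
| Nausea | no | no |
| Myalgia | no | no |

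One of five is named. Neither document has a grouped flu-like term, or a term list that maps the other four symptoms to the allergic/cytokine-release/infusion item.

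**3. Coverage by the fever item on the cited pattern.** Fever is reported as one of the flu-like effects, so at most 5 of the 15 affected volunteers had it: 5/15 = 33%. At least 15 − 5 = 10 (67%) fall outside the fever item. The reaction item could recover some of these. A majority of the 15 means 8, so at least 8 − 5 = 3 of the other 10 would have to be recorded as such a reaction at Grade 2 or above. The documents do not say how severe the volunteers' effects were, so the number cannot be fixed.

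**4. What the ordinary tables can show.** On the same pattern the headache row would hold up to 11 of 15 cases (73%), so much of such a signal would be visible in one line. The participant count still cannot be recovered. From rows of 11 (headache) and 5 (fever), the number with either lies anywhere from 11 (full overlap) to 11 + 5 = 16 (no overlap). Each further symptom row widens the range. Only the listing, or a grouped row, settles it.

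**5. Illustration at low rates.** The rates below are assumptions; the documents give none for XT-150. Take a true flu-like rate r among the 48 active participants, with fever in one third of cases (5/15) and nothing caught by the reaction item. The chance of at least one counted case is 1 − (1 − r)^48 for a grouped row and 1 − (1 − r/3)^48 for fever alone.

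| r | Cases expected | Counted by fever | P(≥1), grouped row | P(≥1), fever alone |
|---|---|---|---|---|
| 5% | 2.4 | 0.8 | 91% | 55% |
| 10% | 4.8 | 1.6 | 99% | 80% |
| 20% | 9.6 | 3.2 | >99% | 96% |

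These chances concern the special-interest count only. The same events would also appear in the general TEAE tables.

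**The case against.** The case against has several parts, and much of it stands.

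- **No literal promise.** Section 4.4.5 says monitoring will be based on earlier reports and, separately, that certain events could be attributed to IL-10v. A reader might infer that the protocol commits to following each symptom as a special-interest event and then breaks that commitment. The text does not say so. Linking the two statements is a fair reading of a section headed as clinical monitoring, and no more.
- **Fever is not the only relevant item.** The Grade 2 reaction item covers events that respond to symptomatic treatment, and the study team reviews special-interest events before unblinding. Some systemic reactions could be caught there. Mild or isolated headache, chills, nausea or myalgia would not be.
- **Nothing is lost.** All AEs are collected, listed and tabulated by arm with a placebo column, and the headache row alone could show most of a signal shaped like the cited one. The gap is in tabulation, not collection. Participants are also observed after each dose, and serum IL-10 is sampled during follow-up.
- **The cited rates do not transfer.** A reader might infer that in a 24-person arm 24 × 15/36 = 10 participants would be affected and only 24 × 5/36 ≈ 3 flagged. The documents do not support this as an expectation, because they put systemic IL-10 exposure more than 1000-fold lower and report no such events in earlier XT-150 studies.
- **A grouped row collects background.** Any-grade headache or nausea over 270 days will occur in every arm and could dilute an acute effect. This is correct, and it is why the row needs a window-restricted count as well as an overall one.
- **Back pain.** The cited study names it as a flu-like effect (3/36), but it is also a symptom of the disease under study. A term list cannot include or omit it without comment.

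**Conclusion.** The point holds in a limited form. Of the five flu-like symptoms that the protocol attributes to a possible IL-10v effect, the special-interest lists name one, and no planned row counts participants with any flu-like reaction. On the cited pattern, the fever item alone covers at most 5 of 15 cases. That ceiling assumes the fever cases are among the flu-like ones, as the text implies, and it leaves out whatever the Grade 2 reaction item would add.

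The stronger conclusion, that the plan would miss most systemic IL-10 effects in this trial, does not follow. Those effects would still appear in the preferred-term tables and listings, and the volunteer data give no usable estimate of how often to expect them here. This is a cheap improvement of low severity that makes the primary safety objective easier to read.

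**What to change.** In SAP 10.14.1, aligned with Protocol 10.7.1, add one grouped special-interest row, *flu-like reaction, any grade*:

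- Fix the preferred-term list before unblinding: headache, pyrexia, chills, nausea, myalgia, influenza-like illness. State how back pain is handled and why.
- Count each participant once, by arm including placebo, both overall and within a pre-specified onset window after each dose received. Some participants receive only the Day 0 dose, so the window must be tied to actual dosing. The sponsor should justify its length, since Protocol 4.1 describes expression over weeks rather than an acute exposure.
- State how partial onset dates are assigned to the window.
- Keep the four existing categories unchanged.

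If the sponsor prefers not to add the row, a sentence saying why the four symptoms were left out of the lists would at least reconcile 4.4.5 with 10.7.1 and SAP 10.14.1.

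The cost is SAP wording, a short term list and one more row in tables already planned. Onset dates are already recorded (Protocol 10.2), so no new data are needed. The downside is that background headache and nausea will enter the row in all arms; the placebo arm and the onset window help to separate them.

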# 4.5. Justification for Dosing Regimen

A standard 1 mL volume of administration will be used for all treatment groups.

# 4.6. Population to be Studied

About 72 adult participants with a diagnosis of moderate to severe pain due to facet osteoarthritis will be enrolled in this study.

# 4.7. Statement of Compliance

This study will be conducted in compliance with the protocol, Good Clinical Practice (GCP), the ethical principles of the Declaration of Helsinki, and applicable regulatory and Institutional Review Board (IRB) requirements.

## 5. STUDY PURPOSE, OBJECTIVES AND ENDPOINTS

The purpose of this study is to gather evidence for the safety, tolerability, and efficacy of XT-150 as a treatment for pain associated with FJOA.

## 5.1. Study Objectives

## 5.1.1. Primary Objective

The primary objective of this study is to evaluate the safety and tolerability of a repeat bilateral intra-articular dose of XT-150.

## 5.1.2. Secondary Objectives

The secondary objective is to establish the analgesic efficacy of a repeat bilateral intra-articular dose of XT-150 as a treatment for pain in participants with facet joint osteoarthritis (FJOA).

## 5.2. Study Endpoints

### 5.2.1. Safety Endpoints

Safety assessments will be recorded throughout the study (up to Study Day 270 [ $\pm$ 14 days]) as described in Table 1. All participants will be assessed for:

- Adverse events (AEs) and serious adverse events (SAEs),
- · Abnormal hematology and chemistry laboratory values,
- · Physical examination findings, and
- Vital signs

following signing of the informed consent form (ICF) and throughout the study until the visit on Day 270  $(\pm 14 \text{ days})$  for each treatment group.

## 5.2.2. Efficacy Endpoints

#### 5.2.2.1. Primary Efficacy Endpoint

The primary efficacy endpoint is change from baseline in pain intensity at Day 270 as recorded on a 0-100 VAS.

#### 5.2.2.2. Secondary Efficacy Endpoints

Secondary efficacy endpoints include:

- Change from baseline in Oswestry Disability Index (ODI) scores
- Change from baseline in Patient Global Assessment scores
- Change from baseline in International Physical Activity Questionnaire (IPAQ) scores

### 5.2.2.3. Exploratory Efficacy Endpoints

Exploratory efficacy endpoints include:

 Change from baseline Short Form Health Survey (SF12) Physical Health Composite Scores (SF-12 PCS) and Mental Health Composite Scores (SF-12 MCS)

### 6. STUDY DESIGN

## 6.1. Description of the Study

This is a Phase 2a, safety and efficacy study of XT-150 in adult participants experiencing back pain due to inflammation of the facet joint (Facet Joint Osteoarthritis [FJOA]) and who are eligible for intra-articular glucocorticoid injection, or radiofrequency ablation of medial branches of the primary dorsal ramus of the exiting nerve root, which innervates the adjacent facet joints.

Participants will provide informed consent and meet all study eligibility criteria before any study procedures are initiated. Baseline assessments for study eligibility will be completed on the same day as or within 1 day before administration of study drug.

Study drug will be administered at Day 0 and Day 90 by intra-articular (IA) injection into the facet capsules, bilaterally at the affected spinal level (e.g. L4-5 and L5-S1). Location responsible for facetogenic pain of the spine will be determined by clinical, radiological and diagnostic (lidocaine) intra-articular injection.

Up to 72 participants will be randomized to one of two dose treatment groups or to placebo (24 participants per treatment group).

- 1. 150 μg XT-150 (1.0 mL total delivered by two 0.5 mL injections)
- 2. 450 µg XT-150 (1.0 mL total delivered by two 0.5 mL injections)
- 3. Placebo (Sterile phosphate-buffered saline for injection, PBS) (1.0 mL total delivered by two 0.5 mL injections).

Following the first treatment with XT-150 or Placebo at Baseline (Day 0), participants will be assessed for safety and efficacy in-clinic on Days 7, 14, 30 and 60. At Day 90, all participants will receive a repeat injection with XT-150 or Placebo based on treatment arm assignment at the time of randomization. Following Day 90, participants will be assessed approximately monthly through Day 270.

Participants who have passed their Day 90 visit or who were enrolled prior to the implementation of Protocol V3.0 08Jun2022 and do not reconsent to a second dose will complete the study at Day 180. During this visit, all End of Study visit activities should be completed.

The Schedule of Assessments and Procedures is presented in Table 1. Day 0 is defined as the day of study drug administration. Subsequent study days are defined by the number of consecutive calendar days after drug administration.

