## 9. STUDY PROCEDURES

Study procedures should be completed within the windows provided in the Schedule of Assessments and Procedures located in Table 1.

A telephone call documenting safety and efficacy assessments may be used for participants unable to physically attend follow up visits due to COVID-19 infection or coronavirus exposure concerns. Home services may be employed for blood collections.

Any nonscheduled procedures required for urgent evaluation of safety concerns take precedence over all routine scheduled procedures.

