## 10.7.2. Localized Signs of Infection or Inflammation at the Injection Site

Events that, in the opinion of the Investigator, may represent localized signs of infection or inflammation at the XT-150 injection site (e.g., pain, erythema, swelling, pruritus, warmth, hematoma, induration) must be recorded as AEs on the CRF. In general, these events will be temporally related to the injection.

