## 12. ASSESSMENT OF ANTI-IL-10 ANTIBODIES

Presence of anti-IL-10 antibodies in serum will be assessed. Whole blood for detection of anti-IL-10 antibodies will be drawn at Baseline, then on Days 7, 14, 30, 60, 90, 180, and 270 then processed to serum. Testing will be conducted following completion of the study.

Procedures for collection, storage, and shipping of immunogenicity samples are described in the study Laboratory Manual.

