## 13. ASSESSMENT OF XT-150 PLASMID DNA BIODISTRIBUTION

Presence of plasmid DNA in whole blood will be assessed. Whole blood for detection of plasmid DNA will be drawn at Baseline, Day 0 + 4 hours, then on Days 7, 14, and 30. Testing will be conducted following completion of the study.

Procedures for collection, storage, and shipping of plasmid DNA samples are described in the study Laboratory Manual.

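### The primary question is repeat-dose tolerability, but the early safety visits and samples follow dose 1 only; the first scheduled visit after the second dosing visit is about 30 days later

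*Protocol*

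**What the plan says.** The primary objective (Protocol 5.1.1) is "to evaluate the safety and tolerability of a repeat bilateral intra-articular dose of XT-150". Injections are given on Day 0 and Day 90.

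- **Visits.** After the first injection, "participants will be assessed for safety and efficacy in-clinic on Days 7, 14, 30 and 60" (Protocol 6.1). After the second: "Following Day 90, participants will be assessed approximately monthly through Day 270". Table 1 shows no visit between Day 90 and Day 120.
- **Day of dosing.** Section 9.3 gives about 4 hours of observation on Day 0. Section 9.4 gives about 1 hour on Day 90, with a site examination and vital signs about 1 hour after injection. The study-drug footnote to Table 1 says 4 hours.
- **Between visits.** Section 9.5 carries that heading but has no readable text.
- **Plasmid DNA** (Protocol 13): whole blood "will be drawn at Baseline, Day 0 + 4 hours, then on Days 7, 14, and 30".
- **Anti-IL-10 antibody** (Protocol 12): blood "will be drawn at Baseline, then on Days 7, 14, 30, 60, 90, 180, and 270". Section 9.4 lists the Day 90 serum before the injection.
- **Local reactions.** Protocol 4.4.6 describes the possibly related events so far as mild, transient injection-site reactions and knee pain. Section 10.7.2 adds: "In general, these events will be temporally related to the injection". SAP 10.14.3 tabulates eight injection-site items by visit.
- **Analysis.** SAP 10.14.1 counts treatment-emergent events from the first dose, with no split by dose. SAP 8 combines one-dose and two-dose participants in the summary tables. SAP 11 confirms that no post-baseline laboratory tests are scheduled.

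**The concern.** SAP 8 records that Protocol Version 3.0 added the second dose during the study. The objective was written for repeat dosing, but the early visits and samples are still placed around the first injection only. The events the protocol leads one to expect are brief and close in time to the injection, which is the period with no scheduled visit after dose 2.

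With no scheduled post-baseline laboratory tests, clinical contact carries most of the safety evidence. A quiet record after the second injection could then be read as good repeat-dose tolerability when part of the quiet comes from not examining early. The argument in Protocol 4.4.4 and 4.4.6 that systemic exposure is low and transient is also not tested in the weeks after the second dose. Section 4.1 says protein is produced over the weeks after injection.

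**Working it through.** The plan gives no figure for the gap after dose 2, so the check is a count from the schedule.

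**1. Windows.** Inputs: Table 1 and Sections 9.4 and 9.6. Day 90 ±7 is 83 to 97 and Day 120 ±7 is 113 to 127. SAP Table 4 lists the same protocol windows. Both are anchored to Day 0.

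- Dose 1 to first visit: 7 ±1 = 6 to 8 days.
- Dose 2 to next visit, nominal: 120 − 90 = 30 days.
- Shortest within windows: 113 − 97 = 16 days.
- Longest within windows: 127 − 83 = 44 days.

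**2. Visits and samples, re-indexed to days since each dose (nominal days).**

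| | After dose 1 | After dose 2 |
|---|---|---|
| Visits within 14 days | 2 (7, 14) | 0 |
| Visits within 30 days | 3 (7, 14, 30) | 1 (30) |
| Post-dose plasmid samples | 4 (4 h, 7, 14, 30) | 0 |
| Serum within 60 days | 4 (7, 14, 30, 60) | 0 |
| All post-dose serum | 5 (adds 90) | 2 (90, 180) |

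The last row uses Days 180 and 270: 180 − 90 = 90 and 270 − 90 = 180. For Day 270, Table 1 lists IL-10 and antibody, while Section 9.7 lists antibody only.

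**3. What a later examination can see.** Take a reaction lasting 14 days or less that is present at the Day 7 examination after dose 1. That examination is on day 8 at the latest, so the reaction started by day 8 and ends by 8 + 14 = day 22. A reaction with the same course after dose 2 is over by a visit at the nominal 30 days, and by any visit more than 22 days after the injection. It need not be over at the shortest gap: onset on day 4 with 14 days' duration runs to day 18, so it is present on both day 7 and day 16.

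**4. Illustration.** Assumptions not in the documents: onset spread evenly over the first 3 days, nominal visit days, visits within 30 days of the dose. Probability that the reaction is still present at a scheduled visit:

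| Duration | Dose 1 | Dose 2 |
|---|---|---|
| 2 or 3 days | 0 | 0 |
| 5 days | 0.33 | 0 |
| 7 or 14 days | 1.0 | 0 |
| 28 days | 1.0 | 0.33 |

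The schedules differ for reactions of about 5 days or longer. Very short ones are missed by the scheduled visits after either dose.

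**5. Whether the tables recover the information.** Treatment-emergent events run from the first dose. Participants who received one dose stay until Day 180, so they contribute to the Day 120, 150 and 180 rows of the injection-site table alongside two-dose participants. The planned tables therefore do not isolate what followed the second injection.

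**The case against.** The strongest reply is that adverse events are still captured. Protocol 10.2 collects them through the last visit with onset and resolution dates. Each visit asks about events since the last one, local signs must be recorded as adverse events (10.7.2), and serious events are reported within 24 hours of site knowledge (10.3). Day 90 has its own site examination, monitoring and vital signs. Section 9.5 is where interim contact would be described, and its text cannot be read. All of this stands. A reader might infer that nobody looks at participants between dose 2 and Day 120, or that second-dose reactions go unobserved. The documents do not support either. What is lost is early examination and accurate timing, not adverse event capture as such.

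A second reply is that every arm follows one schedule and safety is tabulated by arm. That also stands. A reader might infer a bias in favour of XT-150 over placebo, but the shared schedule gives no basis for one. Nor does the readable SAP plan a formal comparison of dose 1 with dose 2.

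Third, plasmid and IL-10 protein are not among the safety endpoints in Protocol 5.2.1, and antibody is sampled at Days 180 and 270, so late antibody formation can still be seen. The gap is confined to early exposure and early immune response. Section 4.4.5 reports none of the listed IL-10-type events after earlier injections, including second ones, but those were in the knee. Section 4.4.1 says effects in facet joint disease had not been explored.

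Finally, the documents give no duration for these reactions, so how many would have resolved by Day 120 is an assumption.

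**Conclusion.** The asymmetry is real and bears on the primary objective. The first scheduled visit after the dosing visit falls at 6 to 8 days for dose 1 and at nominally 30 days (16 to 44) for dose 2. Visits are 2 against 0 within 14 days and 3 against 1 within 30 days. Early plasmid and serum samples are each 4 against 0. The consequence is reduced sensitivity to short-lived reactions after dose 2, and a post-dose-2 incidence that cannot be set beside the dose 1 figure, including in the by-visit table of SAP 10.14.3.

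A reader might go further and say that a reaction of 14 days or less seen at Day 7 could never be seen at Day 120. That is true at the nominal gap but fails at the shortest allowed one.

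The conclusion assumes that Section 9.5 adds no earlier contact. Table 1 and Section 6 show none, but it cannot be excluded. This is a low-cost improvement to how the primary question is answered; it does not invalidate the trial.

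**What to change.** 1. **Safety data collection.** Reconcile what is collected after dose 2 with what is collected after dose 1. One example is brief telephone contacts in the first two weeks after the second injection, recording adverse events and the injection-site symptoms in SAP 10.14.3. Protocol 9 says "A telephone call documenting safety and efficacy assessments may be used", but only for participants who cannot attend because of COVID-19 infection or exposure concerns, so the provision would have to be extended by amendment. Two calls for each of at most 72 participants is at most 144 short calls. Telephone reports are less precise than an examination. Optionally, add plasmid and IL-10/antibody samples at the existing Day 120 visit, at the cost of one blood draw.
2. **Monitoring text.** The Table 1 footnote (4 hours) and Section 9.4 (about 1 hour on Day 90) must be reconciled. The sponsor should also confirm what Section 9.5 provides.
3. **SAP.** Tabulate treatment-emergent events and injection-site signs by days since the most recent injection, and restrict post-dose-2 results to participants who received both doses. This costs programming only.
4. **If no collection is added.** The SAP carries a date of October 2023, so dosing may already be complete. In that case, state in the SAP and CSR that, after the dosing visit, local reactions to dose 2 were first examined at about 30 days and must not be compared with dose 1.
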